#### 11.5.6 Response Review

All responses will be reviewed by the study co-investigator radiologist.

## 12. ADVERSE EVENT REPORTING REQUIREMENTS

### 12.1 General

Adverse event collection and reporting is a routine part of every clinical trial. This study will use the descriptions and grading scales found in the NCI Common Terminology Criteria for Adverse Events version 4.0 (CTCAE v 4.0) that is available at <http://ctep.cancer.gov/reporting//ctc.html>.

Information on all adverse events, whether reported by the participant, directly observed, or detected by physical examination, laboratory test or other means, will be collected, recorded, followed and reported as described in the following sections.

Participants should be instructed to report any serious post-study event(s) that might reasonably be related to participation in this study. The investigator should notify the IRB and any other applicable regulatory agency of any unanticipated death or adverse event occurring after a participant has discontinued or terminated study participation that may reasonably be related to the study.

## 12.2 Definitions

### 12.2.1 Adverse Event (AE)

An adverse event is any undesirable sign, symptom or medical condition or experience that develops or worsens in severity after starting the first dose of study treatment or any procedure specified in the protocol, even if the event is not considered to be related to the study.

Abnormal laboratory values or diagnostic test results constitute adverse events only if they induce clinical signs or symptoms or require treatment or further diagnostic tests.

### 12.2.2 Serious adverse event (SAE)

A serious adverse event is an undesirable sign, symptom, or medical condition which:

- is fatal or life-threatening;
- requires or prolongs inpatient hospitalization;
- results in persistent or significant disability/incapacity;
- constitutes a congenital anomaly or birth defect; or
- jeopardizes the participant and requires medical or surgical intervention to prevent one of the outcomes listed above.

Events **not** considered to be serious adverse events are hospitalizations for:

- routine treatment or monitoring of the studied indication, not associated with any deterioration in condition, or for elective procedures
- elective or pre-planned treatment for a pre-existing condition that did not worsen
- emergency outpatient treatment for an event not fulfilling the serious criteria outlined above and not resulting in inpatient admission
- respite care

### 12.2.3 Expectedness

- Expected: Expected adverse events are those that have been previously identified as resulting from administration of the agent. For the purposes of this study, an adverse event is considered expected when it appears in the current adverse event list, the Investigator's Brochure, the package insert or is included in the informed consent document as a potential risk.

- Unexpected: An adverse event is considered unexpected when it varies in nature, intensity or frequency from information provided in the current adverse event list, the Investigator's Brochure, the package insert or when it is not included in the informed consent document as a potential risk

#### 12.2.4 Attribution

Attribution is the relationship between an adverse event or serious adverse event and the study treatment. Attribution will be assigned as follows:

- Definite – The AE is clearly related to the study treatment.
- Probable – The AE is likely related to the study treatment.
- Possible – The AE may be related to the study treatment.
- Unlikely - The AE is doubtfully related to the study treatment.
- Unrelated - The AE is clearly NOT related to the study treatment.

#### 12.3 Potential Adverse Events

Signs and symptoms of disease progression are not considered AEs. The development of a new cancer should be regarded as an AE. New cancers are those that are not the primary reason for administration of study treatment and have been identified after inclusion of the patient into the clinical study.

Because patients are receiving standard treatments, which are not part of this study, their treating physician will be counseling them on the risk of their treatments, including the risk of surgery, radiation therapy, and/or chemotherapy, whichever is appropriate for the type and the stage of their cancer. The procedures related to the study are phlebotomy, PET imaging (all are optional), SBRT, and Nelfinavir administration.

Phlebotomy can cause pain, bleeding, and rare needle site infection. PET imaging results in low dose radiation exposure (see Investigator's Brochure for details of dosimetry), which has an extremely small risk of causing a secondary cancer.

#### 12.4 Stereotactic Body Radiation Treatment

It is difficult at this time to predict with confidence the complication rate from the proposed SBRT; however, it is reasonable to extrapolate from the current experience with SBRT to the lung and pancreas. One significant toxicity is radiation pneumonitis, which can be manifested as fever, increased exertional dyspnea, pleuritic chest pain, and peritumoral infiltrate on chest imaging. It generally occurs between 1 to 3 months of completion of radiotherapy. The risk of grade 2-4 radiation pneumonitis is approximately 10-15% in patients treated with standard fractionated large field radiotherapy and higher in patients treated with combined chemoradiotherapy. It is highly dependent on the volume of the lung treated to high dose and the mean lung dose. At this point, the incidence of RT pneumonitis from stereotactic radiosurgery for small pulmonary tumors is unknown. However, if the treated tumor volume is kept  $\leq 65$  cc, the risk should be  $< 10-15\%$  with the proposed dose level.

Other toxicities commonly associated with such treatment includes dysphagia, odynophagia, nausea, vomiting, anorexia, and weight loss. Some of these symptoms can also be due to tumor progression. Clinical and radiographic assessments will be performed as indicated to identify all adverse effects, ascertain their etiology, and provide the most appropriate palliative measures. Complications other than radiation pneumonitis, if any, will be graded according to the Common Toxicity Criteria, National Cancer Institute, version 4.0.

## 12.5 Nelfinavir

12.5.1 The safety of VIRACEPT (Nelfinavir mesylate) was studied in over 5000 patients who received drug either alone or in combination with nucleoside analogues. The majority of adverse events were of mild intensity. The most frequently reported adverse event among patients receiving VIRACEPT was diarrhea, which was generally of mild to moderate intensity. The frequency of Nelfinavir-associated diarrhea may be increased in patients receiving the 625 mg tablet because of the increased bioavailability of this formulation.

Adverse events occurring in patients receiving VIRACEPT in all phase II/III clinical trials and considered at least possibly related or of unknown relationship to treatment and of at least moderate severity are listed below:

*Body as a Whole:* abdominal pain, accidental injury, allergic reaction, asthenia, back pain, fever, headache, malaise, pain, and redistribution/accumulation of body fat.

*Digestive System:* anorexia, nausea dyspepsia, epigastric pain, gastrointestinal bleeding, hepatitis, mouth ulceration, pancreatitis and vomiting.

*Hemic/Lymphatic System:* anemia, neutropenia, leukopenia and thrombocytopenia.

*Metabolic/Nutritional System:* increases in alkaline phosphatase, amylase, creatinine, phosphokinase, lactic dehydrogenase, SGOT, SGPT and gamma glutamyl transpeptidase; hyperlipemia, hyperuricemia, hyperglycemia, hypoglycemia, new onset or exacerbation of diabetes mellitus, dehydration, hepatitis, jaundice, and liver function tests abnormal.

*Musculoskeletal System:* arthralgia, arthritis, cramps, myalgia, myasthenia and myopathy.

*Nervous System:* anxiety, depression, dizziness, emotional lability, hyperkinesia, insomnia, migraine, paresthesia, seizures, sleep disorder, somnolence and suicide ideation.

*Respiratory System:* dyspnea, pharyngitis, rhinitis, and sinusitis.

*Skin/Appendages:* dermatitis, folliculitis, fungal dermatitis, maculopapular rash, pruritus, sweating, and urticaria.

*Special Senses:* acute iritis and eye disorder.

*Urogenital System:* kidney calculus, sexual dysfunction and urine abnormality.

12.5.2 The following additional adverse experiences have been reported from post marketing surveillance as at least possibly related or of unknown relationship to VIRACEPT:

*Body as a Whole:* hypersensitivity reactions (including bronchospasm, moderate to severe rash, fever and edema).

*Cardiovascular System:* QTc prolongation, torsades de pointes.

*Digestive System:* jaundice.

*Metabolic/Nutritional System:* bilirubinemia, metabolic acidosis.

- 12.5.3 Human experience of acute overdose with VIRACEPT is limited. There is no specific antidote for overdose with VIRACEPT. If indicated, elimination of unabsorbed drug should be achieved by emesis or gastric lavage. Administration of activated charcoal may also be used to aid removal of unabsorbed drug. Since Nelfinavir is highly protein bound, dialysis is unlikely to significantly remove drug from blood.

## **12.6 Fiducial Implantation**

The risk associated with implantation of fiducials is primarily related to the small risk of pneumothorax associated with percutaneous placement of a needle within the lung. The procedure is analogous to percutaneous needle biopsy, a commonly performed procedure which is associated with a pneumothorax risk ranging from 16-40%. Of patients who develop a pneumothorax, most are managed by observation alone, with only 5-7% of patients requiring intervention such as chest tube placement. Another rare risk of fiducial placement is exacerbation of chronic obstructive lung disease, which may require medical interventions, including rare hospitalization. Other potential complications of fiducial implantation is embolization. In the literature, there is little data regarding this potential complication, but if one were to extrapolate from patients suffering gun-shot wounds to the chest, either with pellets or bullets, standard surgical teaching is not to removal of the small foreign bodies as they rarely cause harm. To further avoid the potential risk of embolization, every effort will be made to place the fiducials in the substance of the tumor rather than in the adjacent lung parenchyma. Theoretically, fiducials implanted elsewhere in the body could embolize to the lungs; to date this has not been reported.

## **12.7 Reporting Procedures**

### **12.7.1 General**

Adverse events will be recorded at each visit. If an adverse event requiring medical attention occurs between visits, this will be recorded as well. The variables to be recorded for each adverse event include, but are not limited to, onset, resolution, intensity, action taken, outcome, causality rating and whether it constitutes an SAE or not. The intensity of the adverse event should be captured using CTCAE criteria, version 4.0, when possible.

Pregnancy should be excluded before enrollment. Pregnancy in itself is not reported as an AE unless there is a suspicion that an investigational product may have interfered with the effectiveness of a contraceptive medication.

All adverse events will be captured on the appropriate study-specific case report forms (CRFs).

### **12.7.2 Institutional Review Board**

All adverse events and serious adverse events will be reported to the IRB per current institutional standards. If an adverse event requires modification of the informed consent, these modifications will be provided to the IRB with the report of the adverse event. If an adverse event requires modification to the study protocol, these modifications will be provided to the IRB as soon as is possible.

## **13. DATA AND SAFETY MONITORING PLAN**

This is a DSMP Level I study under the SKCCC Monitoring Plan (see Appendix II). A Level I study requires both internal and external data monitoring. The Principal Investigator is responsible for internal monitoring for both safety and data quality. External data monitoring will be performed by the SKCCC at Johns Hopkins Clinical Research Office Quality Assurance Program (CRO QA).

Data and safety monitoring oversight will be conducted by the SKCCC at Johns Hopkins Safety Monitoring Committee. Per the SKCCC at Johns Hopkins Safety Monitoring plan, the CRO AQ will forward summaries of all monitoring reports to the Safety Monitoring Committee for review. All reportable anticipated and unanticipated protocol events/problems and amendments that are submitted to the IRB will also be reviewed by the Safety Monitoring Committee Chair (or designee) and QA manager.

## **14. REGULATORY CONSIDERATIONS**

### **14.1 Protocol Review and Amendments**

Information regarding study conduct and progress will be reported to the Institutional Review Board (IRB) per the current institutional standards.

Any changes to the protocol will be made in the form of an amendment and must be approved by the IRB prior to implementation.

### **14.2 Informed Consent**

The investigator (or his/her designee) will explain to each subject the nature of the study, its purpose, the procedures involved, the expected duration, the potential risks and benefits involved and any discomfort it may entail. Each subject will be informed that participation in the study is voluntary, that she may withdraw from the study at any time, and that withdrawal of consent will not affect her subsequent medical treatment or relationship with the treating physician(s) or institution. The informed consent will be given by means of a standard written statement, written in non-technical language, which will be IRB approved. The subject should read and consider the statement before signing and dating it, and will be given a copy of the document. No subject will enter the study or have study-specific procedures done before his/her informed consent has been obtained.

In accordance with the Health Information Portability and Accountability Act (HIPAA), the written informed consent document (or a separate document to be given in conjunction

with the consent document) will include a subject authorization to release medical information to the study sponsor and supporting agencies and/or allow these bodies, a regulatory authority, or Institutional Review Board access to subjects' medical information that includes all hospital records relevant to the study, including subjects' medical history.

### **14.3 Ethics and GCP**

This study will be carried out in compliance with the protocol and Good Clinical Practice, as described in:

1. ICH Harmonized Tripartite Guidelines for Good Clinical Practice 1996.
2. US 21 Code of Federal Regulations dealing with clinical studies (including parts 50 and 56 concerning informed consent and IRB regulations).
3. Declaration of Helsinki, concerning medical research in humans (Recommendations Guiding Physicians in Biomedical Research Involving Human Subjects, Helsinki 1964, amended Tokyo 1975, Venice 1983, Hong Kong 1989, Somerset West 1996).

The investigator agrees to adhere to the instructions and procedures described in it and thereby to adhere to the principles of Good Clinical Practice that it conforms to.

## **15. STATISTICAL CONSIDERATIONS**

### **15.1 Endpoints**

#### **15.1.1 Primary Objective**

To determine the 6-month freedom from local progression of the radiosensitizer Nelfinavir used concurrently with 15 Gy of stereotactic body radiation therapy (SBRT) delivered in 1 fraction (per lesion site) in patients with oligometastatic disease.

#### **15.1.2 Secondary Objectives**

- To describe the toxicity of SBRT combined with Nelfinavir delivered for the population enrolled using grading with CTCAE v. 4.0
- To determine the local control at 6 months after SBRT is delivered to a dose of 15 Gy in 1 fraction (per lesion rate) combined with Nelfinavir in patients with oligometastatic disease.
- To assess long-term clinical outcomes of this patient population after completion of SBRT and Nelfinavir by measuring progression-free survival and overall survival. Progression-free survival will be measured from time of enrollment to date of disease progression or death. Patients who are lost to follow-up will be censored for determination of progression-free survival on the date of their last evaluation. Overall survival is defined as time from enrollment to death due to any cause.
- To assess quality of life following completion of SBRT and Nelfinavir using pre- and post-SBRT completion of the Brief Pain Inventory form which will be filled out by the patient at the treatment response intervals outlined above.

### **15.2 Sample Size/Accrual Rate**

The primary endpoint will be freedom from local progression at 6 months. The treatment regimen would be considered of insufficient activity for further study in this population

if the 6-month FFLP rate is 70% or less, and the minimum required level of efficacy that would warrant further study with the proposed regimen is a 90% FFLP at 6 months. The accrual rate is 3 patients per month, and the patients will be followed for up to 3 years. A total of 42 patients will be entered in the study accounting for a 15% dropout rate. This study would have 90% power to detect an improved 6-month FFLP from 70% to 90% using a two-sided test at significance level 0.05. Alternatively, this corresponds to the power to detect a reduction of hazard rate from 0.06 to 0.02, a reduction of 70% in hazard rate.

There will be no interim analysis for futility, since the progression endpoint will not have been reached by a meaningful number of patients before full accrual.

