### 15.5 Analysis of Primary Objective

The primary efficacy analysis will estimate 6-month freedom from local. Freedom from local progression (FFLP) is defined as the elapsed time from the start date of treatment to the date of documented local. Patients who die without local progression will be censored at the time of death. We will plot the Kaplan-Meier curve for FFLP and estimate 6-month FFLP and its 95% confidence interval based on KM estimate and Greenwood's formula. The analysis population includes all registered subjects who have received at least one fraction of SBRT. Patients that develop distant metastasis before local progression will remain on study.

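### The 6-month Kaplan-Meier analysis planned in 15.5 does not deliver both the 90% power and the two-sided 0.05 level that 15.2 states for 42 patients

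*Combined protocol and SAP*

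**What the plan says.** Section 15.2 defines the endpoint: "The primary endpoint will be freedom from local progression at 6 months". The regimen is judged insufficiently active "if the 6-month FFLP rate is 70% or less", and 90% is the level that would justify further study. On size: "A total of 42 patients will be entered in the study accounting for a 15% dropout rate". On power: "This study would have 90% power to detect an improved 6-month FFLP from 70% to 90% using a two-sided test at significance level 0.05". No test is named. The section then offers a second description of the effect: "this corresponds to the power to detect a reduction of hazard rate from 0.06 to 0.02". Accrual is 3 patients per month, with follow-up of up to 3 years. The timing of dropout is not given.

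Section 15.5 sets the primary analysis, which is to "estimate 6-month FFLP and its 95% confidence interval based on KM estimate" and Greenwood's formula. The scale of the interval is not stated, and no sentence links the interval to a conclusion. On the analysis set: "The analysis population includes all registered subjects who have received at least one fraction of SBRT". On deaths: "Patients who die without local progression will be censored at the time of death". The synopsis hypothesis is that 6-month freedom from local progression (FFLP) exceeds 70%.

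**The concern.** The further-study decision rests on telling 70% from 90%. Section 15.2 tells the reader that a regimen with a true rate of 90% has a 10% chance of being missed, and that one at 70% has a 2.5% chance of passing (the upper half of a two-sided 0.05). Those two figures belong to a test that is not named. The test implied by 15.5 depends on a choice that is not made. At this sample size the choice matters, because the usual interval forms differ in both power and error.

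The choice can also decide the result. Take 7 local progressions among 42 fully followed patients, an observed rate of 83.3%. The lower 95% limit is 72.1% on the plain scale and 70.7% on the arcsine scale, so the regimen passes. It is 69.0% on the logit scale and 68.2% on the log-log scale, so the regimen fails. In a single-arm trial that choice should not be open once the data are seen.

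**Working it through.** **Inputs from 15.2.** Null rate 0.70, alternative 0.90, two-sided 0.05 (z = 1.960), power 0.90 (z = 1.2816), 42 entered, 15% dropout included, accrual 3 per month (42/3 = 14 months).

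**Inputs from 15.5.** KM estimate at 6 months with Greenwood variance. Patients lost before SBRT leave the analysis; later losses are censored.

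**Assumptions, not in the documents.** Success is a lower 95% limit above 70%. FFLP times are exponential, censoring is independent, and dropout follows each of the timings shown below. Deaths are not modelled as extra censoring.

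**Step 1. Where the 42 may come from: a test of the 6-month rate.**

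n = [1.960·√(0.7·0.3) + 1.2816·√(0.9·0.1)]² / 0.2² = 41.1, so 42.

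- Power at 42 is Φ((0.2·√42 − 1.960·√0.21)/0.3) = 90.8%, so the stated 90% is reproduced with no dropout.
- With dropout, 42 × 0.85 = 35.7, about 36. Power at 36 is Φ((0.2·6 − 1.960·√0.21)/0.3) = 84.3%.
- The exact binomial test at 36 passes at 31 or more free of progression. Its upper tail is 2.2% and its power 85.5%.
- The arcsine formula at 36 gives 87.2%.

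**Step 2. Where the 42 may come from: a hazard test.**

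- Monthly hazards are −ln(0.7)/6 = 0.05945 and −ln(0.9)/6 = 0.01756.
- Events needed = [(1.960 + 1.2816)/ln(0.05945/0.01756)]² = 7.07.
- With 14 months' accrual and an assumed 6 further months, the event probability under the alternative is 0.202. Then n = 7.07/0.202 = 35.0, and 35.0/0.85 = 41.1.
- The result depends on that assumed follow-up. For 3, 6, 9 and 12 further months the number after dropout is 52.3, 41.1, 34.2 and 29.5. With the rounded hazards printed in 15.2 and 6 further months it is 45.2.

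Both routes can lead to 42. The first leaves dropout out; the second includes it.

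**Step 3. Power of the 15.5 analysis.** KM and Greenwood were simulated with 42 entered. The log-log, logit, arcsine and plain forms are intervals on those scales. The score form tests 70% using the null variance, with the effective sample size taken from Greenwood. Entries are power at 90% / upper tail at 70%.

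| Form | 15% lost evenly by month 6 | All 15% lost at the start | 15% spread over 3 years |
|---|---|---|---|
| Log-log | 81% / 1.3% | 77% / 1.2% | 87% / 1.6% |
| Logit | 85% / 1.8% | 80% / 1.5% | 88% / 1.7% |
| Score | 87% / 2.1% | 83% / 2.0% | 88% / 1.7% |
| Arcsine | 91% / 3.1% | 89% / 3.3% | 94% / 3.8% |
| Plain | 94% / 4.8% | 92% / 4.9% | 95% / 4.2% |

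A cut-off calibrated to exactly 2.5% under even loss by month 6 gives 88.7% power.

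**Step 4. No dropout at all, n = 42.** Log-log and logit pass at 36 or more: power 87.9%, upper tail 1.5%. Arcsine and plain pass at 35 or more: power 94.6%, upper tail 3.8%. So even with full follow-up none of these four intervals gives both stated figures.

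**The case against.** The case for the plan has four parts.

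1. **The 42 may be right.** Section 15.2 itself mentions hazards, and a hazard test gives 41.1 after dropout if 6 further months are assumed, which is the endpoint's own horizon. A reader might infer that the sponsor forgot to inflate for dropout and that about 50 patients are needed (42/0.85 = 49.4). The documents do not support that inference, because they do not say which test produced the 42. What remains is that the follow-up is an assumption and that a hazard test is not the 15.5 analysis.

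2. **The most literal reading of 15.5 exceeds 90%.** It names Greenwood's formula and no transformation, so the plain interval is a fair reading, and its power is 92-94% with the loss by month 6. A reader might therefore infer from this point that the trial is simply underpowered; that goes too far. What stands is the price: an upper tail of about twice the 2.5% implied by 15.2.

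3. **The shortfall can be small.** A score test with even loss by month 6 gives 87%, and if dropout is spread over 3 years the level-holding forms give 87-88%. This stands, and it is why the size is given as a range.

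4. **The success rule can be inferred** from the 70% benchmark, the two-sided level and the synopsis hypothesis. That is largely true, and the missing rule alone would be a matter of detail. It does not settle the interval form, which decides borderline results.

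**Conclusion.** The concern holds as a mismatch between 15.2 and 15.5. The planned primary analysis does not deliver 90% power and a 2.5% upper tail together. Forms that hold the level give about 77-88% power, so the chance of missing a truly 90% regimen is about 12-23% rather than 10%. The plain interval reaches about 92-94% with an upper tail near 4.8%, and arcsine about 89-91% with a tail near 3.1-3.3%, both if the 15% are lost by month 6.

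These figures rest on the assumptions listed in the working. Dropout timing matters most, and the plan is silent on it. Deaths, which 15.5 censors, would lower power further.

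No arithmetic error in the 42 is established, and nothing here shows that more patients are required. The point should be fixed because a stated operating characteristic is not that of the stated analysis. Confidence is medium, because the test behind the 42 is unknown.

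**What to change.** **In 15.2:** name the test and the follow-up behind the 42, and restate the power for the 15.5 analysis with its dropout-timing assumption. For example: *For the 6-month Kaplan-Meier analysis, with 42 patients entered and 15% lost evenly by month 6, power to show FFLP above 70% when the true rate is 90% is about 85% with the logit interval* (or about 81% with log-log, or about 87% with a null-variance score test).

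**In 15.5:** fix one form that holds the 2.5% upper tail and write the rule. For example: *The 95% confidence interval uses Greenwood's variance on the logit scale. The regimen is considered active if the lower 95% limit for 6-month FFLP exceeds 70%* (or, for the score form, if the test rejects 70%).

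If the sponsor prefers to keep the plain or arcsine interval, 15.2 should print its upper-tail error (about 4.8% or 3.1% with even loss by month 6) beside its power.

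**Cost:** wording in two sections and no added patients. The stated power becomes somewhat lower than 90%, and the log-log and logit intervals are slightly conservative (upper tail about 1.3% and 1.8% with even loss by month 6).
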